1.3 Synopsis

Title:	Phase II Trial to assess the Efficacy of Low Radiation Dose of 20 Gy for the Treatment of Marginal Zone Lymphoma or Follicular Lymphoma Stage I-II localized in the Stomach or the Duodenum
Short Title:	ISRT 20 Gy in Localized Indolent G astric or D uodenal L ymphoma
Acronym	GDL-ISRT 20 Gy
Protocol version identifier:	01, 23.08.2020
Register-No.	NCT04097067 (ClinicalTrials.gov)
Lead Investigators:	[name]. med. [name]/ Dr. med. [name]
Indication/ Medical condition:	Primary indolent (marginal zone or follicular) gastric or duodenal lymphoma
Study Design:	Prospective single-arm multicenter study
Active substance/ Medicinal product	None
Intervention(s):	Involved Site RadioTherapy (ISRT) with 20 Gy
Treatment plan	-Study enrollment, blood draw for biomarker-analysis (at baseline visit/ after 4 Gy/ after 10 Gy / after 20 Gy RT/ at 3 and 6 months after RT) -CT-based planning of RT - ISRT with IMRT (oder 3D-CRT)/ IGRT , daily 2 Gy ad 20 Gy
Objectives:	-Prove the effectiveness of 20 Gy and non-inferiority to 30 Gy with respect to response rate. -Recording of survival rates, quality of life (QoL), radiogenic toxicities and inflammation relevant molecules. -Primary Objective: Response rate 6 months after end of treatment, 4 categories according to GELA-criteria: CR (complete remission) = CR or pMRD (probable minimal residual disease), PR (partial remission) = rRD (responding residual disease), NC (no change), PD (progressive disease) -Secondary Objectives: QoL according to EORTC (QLQ C30 and STO22). EFS=Event-free survival (time to any failure or death from any cause, all patients), PFS=Progression-free survival (time to progression of lymphoma or death from any cause, patients in PR or SD), RFS=Recurrence-free survival (time to recurrence of lymphoma or death from any cause, patients in CR), LSS=Lymphoma-specific survival (time to death related to lymphoma or associated with the treatment, all patients), OS=Overall survival

	
(time to death from any cause, all patients). Level of cytokines IL-1β, IL-4, IL-8, TNFα and other inflammation relevant molecules Syndecan1, MMP-2 and S100 proteins. Acute toxicities during treatment according to NCI-CTC, chronic toxicities according to NCI-CTC/ LENT-SOMA.
 
Monitoring of Adverse Events (AEs) and Serious Adverse Events (SAEs)
 
-Assessment of safety: Monitoring of Adverse Events (AEs) and Serious Adverse Events (SAEs)

Inclusion Criteria:	
 -primary indolent gastric or duodenal lymphoma -pathology: marginal zone lymphoma (MZL) or follicular lymphoma (FL) -stage: clinical stage I or II (Ann Arbor classification) -H. pylori negative or antibiotic resistant lymphoma -any FLIPI score low – high (0-4) -any size of tumor or affected lymph nodes -male or female with age \geq 18 years -performance status ECOG 0 – 3 -written informed consent by the patient
Exclusion Criteria:	
 -prior radiation treatment of the gastrointestinal lymphoma -stage: clinical stage III or IV (Ann Arbor classification)-inability to understand the informed consent or unwillingness to participate in the study -severe comorbidity or organ dysfunction contraindicating the use of RT (liver cirrhosis Child-Pugh C, chronic obstructive pulmonary disease GOLD 4, heart insufficiency NYHA IV, dialysis dependent renal insufficiency, uncontrolled epilepsy) -known seropositivity for HIV -acute hepatitis B or C infection -chronic inflammatory bowel disease -prior malignant disease (exclusion: basalioma, non-metastasized solid tumor in constant remission diagnosed >3 years ago) -pregnancy or breastfeeding -active substance abuse or severely compromised compliance
Statistical Methods:	
Primary endpoint analysis:
 
The primary endpoint is the overall response rate (ORR) 6 months after end of treatment. It will be analysed by a one-sample non-inferiority binomial test. The one-sided significance level is 2.5%, the power is 80%.
 
It will be tested whether ORR will be non-inferior to 0.95, with non-inferiority margin (difference) 0.1, i.e. it will be tested whether the lower limit of the one-sided 97.5% confidence interval by Clopper-Pearson will be greater than 0.85.
 
Secondary endpoint analysis:
 
The pre-specified secondary endpoints will be analysed with appropriate statistical methods depending on the type of variable, e.g. rates are analysed by binomial test and exact 95%-confidence interval, time-to-event endpoints by one-sample log-rank test.

Number of Patients/ Sample size:	
To be assessed for eligibility: n = 88
 
To be assigned to the trial: n = 83
 
To be analyzed: n = 79

Participating Centers:	University Hospitals of: Beijing, Essen, Heidelberg, Kiel, Gießen-Marburg, Muenchen LMU, Muenchen TU, Muenster, New York MSKCC, Rochester, Singapore, Tokyo, Torino, Tuebingen, Boston, San Francisco, Toronto. Other expert hospitals: Bielefeld Franziskus Hospital, Mönchengladbach Kliniken Maria Hilf. Participating (Inter-) national centers after approval of their Ethics Committee/ Institutional Review Board.
Trial duration /Schedule:	Planned recruitment duration: 1.5 years Duration of single patient participation: RT intervention of two weeks plus 6 months after end of treatment Planned overall duration of the study: 2 years Planned start of recruiting/data collection: September 01, 2019 Planned end of data collection: (August 31, 2021) Under the impact of the COVID 19 pandemic the study period will be extended by 6 months until February 28 2022. Planned final report of study results: (August 31 2022) February 28 2023.
Visits:	Visits summary: Baseline visit, first day of RT treatment, second day (after 4 Gy), 5 th day of RT (after 10 Gy), last day of RT (after 20 Gy), 6 weeks after end of RT±5 d, 3 and 6 and 9 months after end of RT±3 weeks, 1 year after end of RT±3 weeks, 2 years after end of RT±3 weeks.
Financial Support:	An application for funding was submitted to the IZKF Muenster and to the DLH-foundation.

1.4 Abbreviations

AE	Adverse Event
ARO	Arbeitsgemeinschaft Radiologische Onkologie
BBB-approach	Bench-Bedside-Bench-approach
CT	Computed tomography
CTC	Common Toxicity Criteria
CTV	Clinical Target Volume
DMC	Data Monitoring Committee
DSGL	German Study Group Gastrointestinal Lymphoma (Deutsche Studiengruppe Gastrointestinale Lymphome)
DVH	Dose Volume Histogram
ECOG	Eastern Cooperative Oncology Group
(e)CRF	(Electronic) Case Report Form
EFS	Event-free survival
ENT	Ear Nose Throat
EORTC	European Organization for Research and Treatment of Cancer
FL	Follicular lymphoma
FLIPI	Follicular Lymphoma International Prognostic Index
GDL	Gastric or Duodenal Lymphoma
GI	Gastrointestinal
GTV	Gross Tumor Volume
Gy	Gray
H.p.	Helicobacter pylori
ICRU	International Commission on Radiation Units and Measurements
IGRT	image guided radiotherapy
ILROG	International Lymphoma Radiation Oncology Group
IMRT	Intensity Modulated Radiotherapy
IPI	International Prognostic Index
IRB	Institutional Review Board
ITV	Internal Target Volume
ISRT	Involved Site Radiotherapy
LN	Lymph Node
LSS	Lymphoma-specific survival
MALT	Mucosa Associated Lymphoid Tissue
MZL	Marginal zone lymphoma
MRD	Minimal Residual Disease
NHL	Non-Hodgkin lymphoma
OS	Overall survival
PET	Positron Emission Tomography
PFS	Progression-free survival
PTV	Planning Target Volume
QoL	Quality of Life
QUANTEC	Quantitative Analysis of Normal Tissue Effects in the Clinic
RFS	Recurrence-free survival
RT	Radiotherapy
SAE	Serious Adverse Event
SOP	Standard Operating Procedure
SUSAR	Suspected Unexpected Serious Adverse Reaction

2 Introduction

2.1 Background Information and Rationale

Primary gastrointestinal lymphomas are rare tumors with an incidence of 0.1-1/100,000 per year. Extranodal indolent lymphomas comprise different histologic subtypes e.g. as marginal zone lymphoma (MZL) or follicular lymphoma (FL). Extranodal MZL most frequently (66%) are located in the gastrointestinal tract, and involvement of the stomach accounts for 30%. Gastrointestinal MZL show low cause-specific mortality rates, they are less likely to relapse than non-gastrointestinal extranodal MZL. MZL often arise multifocally within the stomach. Bowel cases of gastrointestinal FL are most common (63%), followed by gastric cases (18%). Bowel cases of FL have better outcomes (5-year OS = 81%, $p < 0.001$) in comparison to gastric FL cases (5-year OS = 53%). Gastrointestinal lymphomas (GIL) represent a low risk of distant dissemination.

Actual guidelines on gastrointestinal indolent lymphoma favour an organ-preserving approach. The standard treatment of *Helicobacter pylori* (HP) positive gastric lymphoma is an antimicrobial therapy. In case of persisting lymphoma after HP eradication and in case of HP-negative lymphoma patients are treated with local radiation therapy with curative intent. For indolent lymphoma of the bowel surgical treatment is limited to rare complications (perforation or bleeding). Depending on the primary localization and extent of the disease uncomplicated indolent lymphomas of the bowel are treated with local (NHL confined to duodenum) or locoregional "whole abdominal" (NHL of the small bowel or duodenal lymphoma with confirmed/ suspected involvement of small bowel) radiation therapy.

For extranodal indolent Non Hodgkin lymphoma regardless of the localization the radiation dose range is currently reported between 20 and 30 Gy (Lowry 2011). The actual guidelines of the International Lymphoma Radiation Oncology Group (ILROG) for radiation dose given to extranodal indolent non Hodgkin lymphoma (NHL) by Involved Site Radiotherapy (ISRT) are 24-30 Gy depending on the diseased organ, for gastric and duodenal lymphoma 30 Gy are recommended (Yahalom 2015).

As known from previous publications, radiation doses of ≥ 20 Gy do not impair tumor control in indolent NHL. In a retrospective series of 496 irradiated patients from Toronto (1967-1978), the radiation doses applied to fields of involvement were subgrouped in the range from < 20 Gy up to > 40 Gy. Radiation dose did not exert a significant effect upon local tumor control particularly in low grade lymphoma. For the included 143 patients with localized low grade lymphoma (nodal and/ or extranodal sites) the analysis of outcome by radiation dose failed to indicate a dose-control relationship in the range from 20 to 40 Gy. Dose-response reached a plateau at 20 Gy for indolent non Hodgkin lymphoma with an increase of relative risk of relapse in the subgroup of < 20 Gy (Sutcliffe 1985). In a current large multicenter randomized controlled trial (United Kingdom) lower RT doses of 24 vs. 40-45 Gy showed no loss of efficacy in patients with indolent non Hodgkin lymphoma of various sites (predominantly follicular and marginal zone) regarding ORR/ in-field progression/ PFS/ Overall survival (Lowry 2011). International publications keep showing an obvious tendency towards lower radiation doses in extranodal indolent non Hodgkin lymphoma (NHL) of various sites. The multicenter randomized 4 Gy vs. 24 Gy FORT trial at 614 manifestations of indolent NHL (including FL $n=469$, MZL $n=72$) has been shown 4 Gy to be effective but resulting in significant lower tumor control in FL, whereas a clear but not significant difference between 4 and 24 Gy resulted for the small subgroup of MZL (Hoskin 2014).

Extranodal MZL of the stomach are significantly less likely to relapse or progress, compared with primaries in other extraintestinal organs (Teckie 2017). Extranodal FL of the duodenum

are associated with better progression-free survival (PFS) than those of other parts of the GI-tract (Harada 2016).

For indolent gastric lymphoma in the literature of the past 25 years efficient radiation doses of 20-46 Gy are documented; 20 Gy achieved complete remission in small patient numbers (Tsang 2001).

Since our current state of knowledge tells us that RT doses from 20 to 40 Gy reach a consistent tumor control in a variety of (extra-)nodal indolent lymphoma, in this trial the effectiveness of 20 Gy will be verified for gastric/duodenal indolent lymphoma in a prospective stratified design using the modern radiation technique ISRT. This trial addresses the research question, if 20 Gy ISRT is not relevantly inferior to the currently recommended standard dose of 30 Gy in GIL of the stomach or duodenum in respect to the remission rate. A complete or partial response to RT alone with a median dose of 30 Gy was achieved in at least 95% of patients with early-stage extranodal marginal zone lymphoma at different anatomical sites (Tsang 2003, Teckie 2015).

Based on the current findings, that gastrointestinal indolent B-cell lymphoma could develop against the background of an inflammatory microenvironment with proinflammatory cytokines found to be elevated particularly in gastrointestinal FL and MALT lymphoma (Miyata-Takata 2015), and that ionizing radiation therapy can modulate anti-tumor immune responses (Di Maggio 2015), additional analysis of inflammation relevant molecules is projected in this study. Serum levels of certain cytokines and inflammatory molecules will be determined before and after predefined radiation doses and during follow-up (see chapter 3.1.3. Additional Research Program) to be correlated with histologic subtype and tumor control of GI-lymphoma. This multiparametric approach allows to identify potential targets that may affect radiation-response in GI-lymphoma. Additional analysis of inflammation relevant biomarkers – correlation with lymphoma subtype and tumor control after radiotherapy – identification of targets for radiation dose-response, these steps together provide the specific Bench-Bedside-Bench(BBB)-approach of this trial.

2.2 Risk-Benefit Analysis

In terms of eradicating the lymphoma disease with 20 Gy, patients with GIL could be cured within a two-week course of RT with as few as possible side effects (adverse effects of radiotherapy are dose-dependent). In the unlikely event of persisting disease, patients have the safe option of further RT, a renewed radiation dose of 20-30 Gy would be feasible. Large studies conducted in Australia, Germany and the Netherlands particularly in gastric indolent lymphoma were continued with highly effective doses of at median 40 Gy at once.

During the study for each patient the risk-benefit balance will be analyzed.

The appropriate therapy according to the lowest possible RT dose can have substantial influence on the therapy costs as well as on the therapeutic success. The trial design offers the opportunity to define a new standard RT dose for GIL worldwide.

The potential benefit for the participant/patient concerned is great by having low toxicity and short treatment duration as well as the good prospect of cure.

3 Objectives and Endpoints

3.1 Objectives

3.1.1 Primary Objective

The primary objective is to demonstrate the efficacy and safety of the low-dose RT concept with 20 Gy (10x2 Gy). Therefore, the overall response rate (ORR) to radiation treatment is

examined to evaluate whether the interventional administration of 20 Gy is not relevantly inferior to international standard dose of 30 Gy.

3.1.2 Secondary Objectives

The secondary objectives are the recording and analysis of the following criteria: quality of life and survival rates (event-free survival, lymphoma specific survival, progression-free survival, overall survival). During and after radiation treatment the acute and chronic adverse effects, including possible Adverse Events (AEs) and Serious Adverse Events (SAEs) will be collected.

Certain inflammatory cytokines are known to be elevated in patients with low-grade gastrointestinal lymphoma. In addition, cytokine profiles after radiation exposure are dose dependent. The effects of the radiation dose regimen on the production of cytokines (IL-1 β , IL-4, IL-8, TNF α) and other inflammation relevant molecules (Syndecan1, MMP-2 and S100 proteins) are to be investigated. Determination of the relationship between radiation exposure, inflammatory response and (complete) remission rate of each gastrointestinal lymphoma subtype is intended in order to optimize and personalize radiation therapy treatment for each patient.

3.1.3 Additional Research Program (Bench-Bedside-Bench-approach)

Serum samples for Research Program are analyzed at the University of Muenster!

The following inflammation related molecules should be quantified in serum samples of patients six times: prior, during (after 4 Gy, after 10 Gy, after 20 Gy) and at 3 and 6 months follow-up visit after radiation treatment. In the radiobiology lab Muenster the cytokines IL-1 β , IL-4, IL-8, TNF α as well as the proteins Syndecan1 and MMP-2, in the immunology lab Muenster additionally S100 proteins are tested.

Magnetic Luminex Assay (R&D Systems) will be used to quantify these biomarkers in serum samples in the radiobiology lab at the University Hospital Muenster. Concentrations of S100A8/ S100A9 are quantified by an in-house ELISA.

Blood collection:

- 15 - 18 ml blood should be collected by venipuncture using two 7.5 - 9 ml serum monovettes with clotting activator (e.g. Sarstedt, Nümbrecht, Germany; order no: 02.1063.001)
- for clotting of blood, samples should be stored at room temperature for 20-30 minutes.

Serum isolation and storage in the central laboratory of the clinic:

- monovettes should be centrifuged for 10 min. at 1500 x g
- Serum (supernatant) should be aliquoted by pipetting about 1ml of the serum into separate 2 ml cryotubes or 2ml Eppendorf reaction tubes, so that at least 4 serum aliquots are available from each blood withdrawal (attention: to avoid cellular contamination, release of half a centimeter of serum is indicated and pipette should not put deeper than half a centimeter over pellet into the monovette)**
- Instead of Eppendorf reaction tubes (e.g. Eppendorf, Wesseling-Berzdorf, Germany) also cryotubes (e.g. Diagonal, Muenster, Germany) can be used.
- The aliquots should immediately be stored **at least at -20 °C in a freezer**.
- Repeated freeze-thaw cycles should be avoided and the time from blood collection to freezing of serum should not take longer than 40-60 minutes.
- Labeling of serum samples** in accordance with the **6 visit dates 'baseline, 4 Gy, 10 Gy, 20 Gy, 3 months, 6 months':**
- 'Country_center-patient-visit'**
- >e.g. 'G001-001-baseline'** (G=Germany, 001=Muenster, 001=first patient, baseline visit).

For shipment, samples should be put in a fitting small box and placed in a bigger polystyrene box together with about 6kg dry ice. The box should be sealed with adhesive tape.

Each participating clinic stores its serum samples at the longest until the end of patients acquisition. By each center at two different times (in the second half of the first year, and after the end of recruitment) the samples are sent on dry ice to the radiobiology lab in Muenster, and from there are also forwarded to the immunology lab, in each of which the analyses will be carried out.

In the radiobiology lab the serum samples will be analyzed by using Magnetic Luminex Assay as described by the manufacturer (R&D Systems, Minneapolis Minnesota, USA). A detailed assay instruction can be found at <https://resources.rndsystems.com/pdfs/datasheets/lxsahm.pdf> and https://www.rndsystems.com/products/human-magnetic-luminex-assay_lxsahm#product-datasheets. The measurement takes place on a Luminex analyzer (Luminex LX200). These analyses should be used to measure the concentration of the six defined biomarkers in serum samples of lymphoma patients in relation to 20 Gy radiation treatment. In the immunology lab additional markers, as S100 proteins, will be quantified.

Biomarker values should be determined prior (baseline visit), during (**after 4 Gy, after 10 Gy**) and directly **after** radiation therapy of 20 Gy, and 3 and 6 months after therapy. The quantitative analysis of the selected biomarkers should give information about the efficacy of the (4 Gy/ 10 Gy/ 20 Gy) radiation treatment concept to activate inflammatory and immunological relevant processes in relation to oncological disease response and subtype of GI-lymphoma.

Research Program – Hypotheses:

- Serum IL-1 β , IL-4, IL-8, TNF α , Syndecan1, MMP-2 and S100 proteins are elevated in MZL
- Serum IL-8, TNF α , Syndecan1, MMP-2 and S100 proteins are elevated in FL
- Antibiotic-resistant H. pylori-positive status of patient is associated with higher elevation of serum-biomarkers than H. pylori-negative status
- Radiotherapy causes directly a radiation dose-dependent elevation of serum-biomarkers in MZL and FL
- The immediate radiogenic elevation of serum-biomarkers is more pronounced in MZL than in FL
- The immediate radiogenic elevation of serum-biomarkers is more pronounced in gastric-NHL than in duodenal-NHL
- The immediate radiogenic elevation of serum-biomarkers correlates directly proportional to tumor control after radiotherapy
- After radiotherapy at follow-up vs. baseline a decrease of serum-biomarkers is shown in MZL and FL
- Post-radiogenic decrease of serum-biomarkers at follow-up vs. baseline is more pronounced in MZL than in FL
- Post-radiogenic decrease of serum-biomarkers at follow-up vs. baseline is more pronounced in gastric-NHL than in duodenal-NHL
- Post-radiogenic decrease of serum-biomarkers at follow-up vs. baseline correlates directly with tumor control after radiotherapy

3.2 Endpoints

3.2.1 Primary Endpoint

-Overall response rate ORR (CR+PR) \geq 95%, 6 months after the end of treatment.

-4 categories of response, according to **GELA-criteria**: **CR** (complete remission) = CR or pMRD (probable minimal residual disease), **PR** (partial remission) = rRD (responding residual disease), **NC** (no change), **PD** (progressive disease)

3.2.2 Secondary Endpoints

-**Quality of life** (QoL) according to EORTC (QLQ C30 and STO22), at baseline visit/ after 20 Gy (=last day of RT)/ 6 months after end of RT.

-**EFS**=Event-free survival (time from beginning of RT to any failure or death from any cause, all patients). Follow-up over 2 years after end of RT.

-**PFS**=Progression-free survival (time from beginning of RT to progression of lymphoma or death from any cause, patients in PR or SD). Follow-up over 2 years after end of RT.

-**RFS**=Recurrence-free survival (time from beginning of RT to recurrence of lymphoma or death from any cause, patients in CR). Follow-up over 2 years after end of RT.

-**LSS**=Lymphoma-specific survival (time from beginning of RT to death related to lymphoma or associated with the treatment, all patients). Follow-up over 2 years after end of RT.

-**OS**=Overall survival (time from beginning of RT to death from any cause, all patients). Follow-up over 2 years after end of RT.

-Level of **cytokines IL-1 β , IL-4, IL-8, TNF α** and other inflammation relevant molecules: **Syndecan1 and MMP-2** and **S100 proteins** at baseline visit/ after 4 Gy/ after 10 Gy/ after 20 Gy on last day of RT/ at 3 and 6 months after end of RT.

-**Acute toxicities** during treatment, 6 weeks after end of RT, according to NCI-CTC

-**Chronic toxicities** from 3 months up to 2 years after end of RT, according to NCI-CTC/ LENT-SOMA.

-Incidence of **Adverse Events** (AEs) and **Serious Adverse Events** (SAEs), continuously.

4 Study Design

-Single-arm, prospective, open label, interventional, multicenter study.

-Historic data from irradiated patients with indolent gastrointestinal lymphomas serves as a basis for the intended response rate.

-Participation of further international sites with expertise in radiation treatment of gastrointestinal lymphomas after approval of their Ethics Committee/ IRB.

-Number of 79 patients need to be analyzed.

-Justification for 'single-arm design' and for 'non-inferiority limit': the low prevalence of the disease, the limited risk of the study design (because of the option of renewed RT in case of persisting disease) and the benefit in terms of lower risk of adverse reactions due to the lower RT dose of 20 Gy in comparison to standard dose of 30 Gy.

5 Study Sites and Study Population

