8.3.2 FU-2 – FU-6

The further exams take place quarterly in the first year after treatment (FU-2 – FU-5), afterwards an annual visit is scheduled (FU-6).

FU-2:	3 months after end of RT ± 3 weeks
FU-3:	6 months after end of RT ± 3 weeks
FU-4:	9 months after end of RT ± 3 weeks
FU-5:	12 months (1 year) after end of RT ± 3 weeks
FU-6:	24 months (2 years) after end of RT ± 3 weeks

The FU-2 and FU-3 visits include blood draw!

At all follow-up visits (FU-2 – FU-6) chronic radiogenic reactions must be documented (see Appendix 16.6 Adverse Reactions according to LENT SOMA).

Each follow-up visit consists of the following examinations:

- Anamnesis
- Clinical examination: ECOG, weight, blood pressure
(at FU-1/-2/-3/-5/-6)
- Quality of life assessment with QLQ-C30 and STO-22 (at FU-1/-2/-3)
- Endoscopy/ Endosonography (+ biopsies) (at FU-2/-3/-5/-6)
- CT-imaging (at FU-3/-5/-6)
- **Blood draw (at FU-2/-3):**
 - o –Routine: small blood count, LDH, GOT, GPT, alcalic phosphatase, γ-GT, bilirubin, creatinine.
 - o –**Research program (analyses at the University of Muenster!):**
Two 7.5 - 9 ml serum monovettes.
Centrifugation, freezing and storage see 3.1.3 and Appendix 16.7 (SOP BLOOD SAMPLES for RESEARCH PROGRAM)
Transmission of frozen blood samples to Radiobiology lab, Muenster at the cost of Dept. of Radiation Oncology, University Hospital Muenster
- Chronic radiogenic reactions must be documented (see Appendix 16.6 Adverse Reactions according to LENT SOMA)

The FU-6 is the study termination visit and ends the study regularly.

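### PFS and RFS are restricted to response groups known only months after RT, yet both are timed from the start of RT, so primary progressions and early deaths fall outside both endpoints

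*Protocol*

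**What the plan says.** Protocol section 3.2.2 lists two response-restricted survival endpoints:

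- "Progression-free survival (time from beginning of RT to progression of lymphoma or death from any cause, patients in PR or SD")
- "Recurrence-free survival (time from beginning of RT to recurrence of lymphoma or death from any cause, patients in CR")

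Both have follow-up to 2 years after the end of RT. The synopsis (1.3) repeats the two populations. The all-patient counterpart in 3.2.2 is "Event-free survival (time from beginning of RT to any failure or death from any cause, all patients"); OS and LSS are also defined for all patients.

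Section 3.2.1 gives "4 categories of response, according to GELA-criteria", namely CR, PR, NC and PD, for a primary endpoint assessed "6 months after the end of treatment". Section 8.3.2 schedules "Endoscopy/ Endosonography (+ biopsies) (at FU-2/-3/-5/-6"), and FU-2 falls at "3 months after end of RT ± 3 weeks".

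For analysis, the synopsis gives as an example "time-to-event endpoints by one-sample log-rank test". Section 11.3 treats everything beyond the primary analysis as exploratory.

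**The concern.** Membership of the PFS and RFS sets is decided by an outcome observed after RT, while time is counted from the start of RT. Two things follow.

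1. Some patients belong to neither set: those with PD at the assessment that decides membership, and those who die before it. PFS then leaves out primary progression, which a reader would expect it to count.
2. Every patient who does enter a set must have been alive and free of progression or recurrence up to that assessment. The early part of each curve is flat by construction (immortal time).

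At stake is the reading of durable lymphoma control in a trial that, according to section 2.2, could define a new standard dose. A curve labelled PFS or RFS will be compared with published series, and a reader may not notice that early failures were removed by definition.

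**Working it through.** **The plan's own figures.** The protocol gives no event number, reference rate or power for PFS or RFS. The only sized endpoint is ORR. Its 79 patients reproduce: ((1.96·√(0.85·0.15) + 0.8416·√(0.95·0.05)) / 0.10)² = 78.02, so 79. The exact rule (at least 74 responders) has power 0.797. Nothing below depends on this.

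**Who is in which set at the classifying assessment**

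| Status | PFS set | RFS set | EFS |
|---|---|---|---|
| CR | no | yes | yes |
| PR | yes | no | yes |
| NC (if this is what SD means) | yes | no | yes |
| PD | no | no | yes |
| Died before assessment | no | no | yes |

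SD is not one of the four labels in 3.2.1, so the third row is itself an interpretation.

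**Guaranteed event-free time.** Inputs: ten daily fractions over two weeks, taken as 12 calendar days (12/30.44 = 0.39 months); FU-2 at 3 months and FU-3 at 6 months after RT, each ± 3 weeks (0.69 months); follow-up to 24 months after RT, so 24.39 months from RT start.

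- Status set at FU-2: 0.39 + 3 = 3.39 months (window 2.7 to 4.1), or 3.39/24.39 = 14% of follow-up.
- Status set at FU-3: 0.39 + 6 = 6.39 months (window 5.7 to 7.1), or 6.39/24.39 = 26%.

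The choice of visit is inferred from the schedule; the protocol names none.

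**Effect on the curve (illustration).** Assume a constant hazard λ. With T = 24.39 and L the classification time, a true 2-year event-free proportion S appears as exp(−λ(T − L)), where λ = −ln S / T. The values of S are assumptions, not in the protocol.

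| True S | Appears as, FU-2 | Appears as, FU-3 |
|---|---|---|
| 0.95 | 0.957 | 0.963 |
| 0.90 | 0.913 | 0.925 |
| 0.80 | 0.825 | 0.848 |

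Front-loaded failures act through the same exclusion and are not additional. If 4 of 79 patients failed before classification and 0.90 of the other 75 were event-free at 2 years, the all-patient figure would be 75/79 × 0.90 = 0.854.

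**Effect on a one-sample log-rank test (illustration).** Assume further that the reference is an all-patient curve timed from RT start and that the true hazard equals the reference. Per patient in the set, observed O = 1 − exp(−λ(T − L)) and expected E = O + λL, because λL accrues while no event is possible.

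- S = 0.90, FU-2: λ = 0.00432; O = 0.0867, E = 0.0867 + 0.0147 = 0.1014; O/E = 0.855.
- S = 0.90, FU-3: O = 0.0748, E = 0.0748 + 0.0276 = 0.1024; O/E = 0.730.
- Over S from 0.80 to 0.95: 0.849 to 0.858 (FU-2) and 0.722 to 0.734 (FU-3).
- Simple person-time shares, ignoring RT duration: 21/24 = 0.875 and 18/24 = 0.75.

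Even with 79 patients in one set, more than either would hold if both were populated, (O − E)/√E on totals runs from −0.28 (S = 0.95, FU-2) to −1.13 (S = 0.80, FU-3). In this illustration the artefact shifts the test but does not reach significance alone.

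**The case against.** The strongest reply has four parts.

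- **Early failures are not lost to the trial.** Success is decided by ORR under ITT, where NC and PD are not responses. EFS counts any failure or death in all patients from RT start, and OS counts all deaths. Section 11.3 makes PFS and RFS exploratory. All of this stands and limits the harm, but it does not make the two definitions sound.
- **The size of the bias depends on things the protocol does not state.** No classifying visit and no reference curve is given. If the reference used the same response-defined sets and time origin, the bias would largely cancel. A constant hazard is also doubtful: the first scheduled endoscopy is at 3 months, so few progressions would be recorded before then in any cohort restaged on a similar schedule. This stands; the ratios are conditional illustrations.
- **The log-rank test is only an example in the synopsis.** Its reference and reporting details can properly be left to a SAP. This stands for the test. Population and time origin, however, are fixed explicitly in 3.2.2.
- **Not every progression is missed.** A reader might infer that all PD cases, up to 79 − 74 = 5 in a successful trial, vanish from PFS. The documents do not support that. Five is a ceiling on all non-responders, including NC, who would be inside the PFS set if SD means NC. If status is set at FU-2, a patient in PR or SD then who has PD at FU-3 is counted as a PFS event.

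**Conclusion.** The definitions are wrong as written. They select on post-RT response, start the clock at RT, and name no classifying visit or landmark. That PD at classification and death before it fall outside both sets, and that each set has guaranteed event-free time, follows from the text without further assumptions. The length of that time, about 3.4 or 6.4 months, is inferred from the visit schedule.

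Both curves are therefore too favourable as estimates from RT start. A one-sample log-rank test would be biased towards 20 Gy if its reference were unconditioned and timed from RT. Observed/expected of about 0.85-0.88 (FU-2) or 0.72-0.75 (FU-3) illustrates this under an assumed constant hazard and assumed 2-year rates; neither is a prediction for this trial.

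A reader might go further and conclude that the trial's main result is tilted towards success. It is not: the ORR test does not use these endpoints. The point concerns two exploratory endpoints and is worth correcting because the correction is cheap and the labels invite misreading.

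**What to change.** Amend section 3.2.2 and the matching synopsis entries:

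- **PFS:** all patients, from start of RT to progression, relapse or death from any cause.
- **RFS:** patients in CR, timed from first documented CR, or from a named landmark visit (for example FU-3) among patients in CR and under follow-up at that visit.
- **One-sample log-rank test:** only where the reference curve has the same population and time origin.
- **Labels:** use NC in place of SD, or state that they are the same, so that 3.2.1 and 3.2.2 agree.

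The cost is wording only: no new visits, data or patients. There are two downsides. PFS in all patients will overlap heavily with EFS. RFS will have somewhat shorter follow-up, about 24.4 − 6.4 = 18 months with an FU-3 landmark, or about 21 months for a CR first documented at FU-2.
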